8.5 Primary Efficacy Endpoint

The primary efficacy endpoint in this evaluation will be a comparison of the reported Snellen distance visual acuities as associated with the Test and Control lenses during scheduled visits. It is expected that the lens Snellen distance visual acuity results will be substantially equivalent between the Test and the Control lenses.

The visual acuity measurements will be recorded using a standard Snellen VA chart calibrated for an effective visual distance of 20 feet.

The visual acuity measurements will be analyzed using the relative comparative distribution of the visual acuity reports across the Test and Control lens groups.

In addition, the lens visual acuity at the final study visit will be compared to the over refractive lens visual acuity at the Training-Dispensing visit and the changes (≥ 2 line change) assessed and compared across the Test and the Control Lens groups. It is expected that the results of both analysis will be substantially equivalent between the Test and the Control Lenses.

[REDACTED]

[REDACTED]

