5.4.2 Efficacy Endpoints

The primary efficacy endpoint in this evaluation will be a comparison of the reported Snellen distance visual acuities as associated with the Test and Control lenses during scheduled visits. It is expected that the lens Snellen distance visual acuity results will be substantially equivalent between the Test and the Control lenses.

In addition, visual acuity with the Test and Control Lenses at the final study visit will be compared to the Test and Control Lens visual acuity at the Fitting visit. All changes ≥ 2 lines of visual acuity will be explained and compared across the Test and the Control lens groups. It is expected that the results will be substantially equivalent between the Test and the Control lens groups.

[REDACTED]

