6.2.2 Randomization/Trial Fitting

If a subject is found to be eligible and expresses interest in participating in the study, the subject will be randomized into one of the study materials. The appropriately randomized material will be placed on the subject’s eyes by the study coordinator or by the subject under the study coordinator’s supervision. An evaluation of the lens visual acuity, over refraction, resulting visual acuity and lens fit will be performed by a licensed investigator following 10 minutes of adaptation. Up to three lenses per eye may be used to optimize the visual acuity.

Subjects can only be considered for lens training/dispensing if:

1. They have an acceptable or optimal fit as judged by a licensed investigator and
2. Their Snellen Visual Acuity with the study lenses is equal to or better than 20/30 in each eye.

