e Adverse Event forms must be completed at any time an adverse event is noted and each time the subject is evaluated until the event is resolved.

f Visual acuity **must be** recorded at **every** visit for **each** eye with either contact lenses, glasses or unaided.

g As Appropriate

* Subjective Assessment is captured as part of the Training/Dispensing Form.

** Fitting and Surface Evaluation information is collected as part of the Fitting Form

Table 3 Evaluation/Measurement/Information Collected

Evaluation/Measurement/Information to be Recorded		Initial, Fitting, Training/Dispensing Visits			Follow-up Visits		Exit Visit
		Initial	Fitting	Training/Dispensing	Scheduled	Unscheduled	
Informed Consent		X					
Randomization			X ^c				
Eligibility Evaluation	Inclusion Criteria	X	X	X			
	Exclusion Criteria	X					
Subjective Acceptance	Habitual Lens	X					
	Study Lens			X	X	X ^b	
Symptoms		X			X	X ^b	
Subject Medical History and Demographics		X					
Habitual Lens VA, Lens Wearing History and Habits		X					
Spectacle or Unaided VA						X ^f	
Manifest Refraction, Best Spectacle-Corrected VA or Unaided VA		X				X	X
Lens VA & Over-Refraction, Best Corrected Lens VA			X		X	X ^b	
Keratometry		X					X
Slit Lamp		X	X ^g	X ^g	X	X	
[REDACTED]		■			■	■	
[REDACTED]		■			■	■	
[REDACTED]			■		■	■	
[REDACTED]			■		■	■	
[REDACTED]			■	■	■	■	
Adverse Event Documentation		X ^e	X ^e	X ^e	X ^e	X ^e	X ^e
Reason for Exit		X ^a	X ^a	X ^a	X ^a	X ^a	X ^a

Refer to Legends from Table 2

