8.2 Sample Size Justification

The completed subjects sample size for this study is planned to be 50 Test Lens subjects and 25 Control Lens subjects based on a two to one (2:1) ratio of Test Lens subjects to Control Lens subjects.

The sample size for this study is based on the ISO 11980:2012 Ophthalmic optics – Contact lenses and contact lens care products – Guidance for clinical investigations.

Expected drop-out rates for both the Test and the Control lenses are calculated to be approximately 15%.

Due to the limited sample sizes required for this study the power calculations and level of significance are not appropriate for calculation. Differences between the results for the Test and Control cohorts will be evaluated based on clinical judgments.

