8.7.6 Treatment of Missing, Unused or Spurious Data

The analysis set will be the full analysis set, which consists of all subjects randomized into the study with an actual lens dispensed. Discontinued subject data will be analyzed separately from the completed subject data.

Missing data will be accounted for in the sample size accounting.

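### Sections 5.4.2 and 8.5 give different baselines for the 2-line acuity-change analysis, and 8.5 sets lens-only acuity against over-refracted acuity

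*Combined protocol and SAP*

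**What the plan says.** Sections 5.4.2 and 8.5 both add the same supporting analysis to the main efficacy comparison: acuity at the final visit against an earlier acuity, with changes of at least 2 lines compared between arms.

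- **Section 5.4.2** takes final-visit acuity with the study lenses, "compared to the Test and Control Lens visual acuity at the Fitting visit". It adds that all changes of at least 2 "lines of visual acuity will be explained and compared across the Test and the Control lens groups".
- **Section 8.5** says "the lens visual acuity at the final study visit will be compared to the over refractive lens visual acuity at the Training-Dispensing visit". It uses the same 2-line threshold but does not repeat the commitment to explain each change.

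Elsewhere the plan treats lens acuity and over-refracted acuity as separate readings. Section 6.2.2 says of the trial fitting: "An evaluation of the lens visual acuity, over refraction, resulting visual acuity and lens fit will be performed". Table 3 in section 6.3.3 has a row "Lens VA & Over-Refraction, Best Corrected Lens VA". It is marked at Fitting and at scheduled and unscheduled follow-up; the Training/Dispensing cell appears blank.

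On numbers, section 8.2 states: "The completed subjects sample size for this study is planned to be 50 Test Lens subjects and 25 Control Lens subjects". It gives no power or significance level and leaves differences between arms to clinical judgment.

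**The concern.** The two sections specify one analysis with two baselines. An analyst following 5.4.2 and one following 8.5 can list different eyes as changed, and the choice could be made after the data are seen.

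The 8.5 form has a further fault of its own. Over-refraction adds the best residual correction over the lens, so the resulting acuity is normally as good as or better than acuity with the lens alone. If the first is the baseline and the second the outcome, every eye that benefits from over-refraction starts with an apparent loss. Losses are overstated and gains are hidden.

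Because the plan makes no formal test, descriptive counts such as these are what a reader will judge.

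**Working it through.** **1. The two definitions side by side**

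| | Section 5.4.2 | Section 8.5 |
|---|---|---|
| Outcome | lens acuity, final visit | lens acuity, final visit |
| Baseline visit | Fitting | Training-Dispensing |
| Baseline measure | lens acuity | over-refracted lens acuity |
| Threshold | at least 2 lines | at least 2 lines |

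Outcome and threshold agree; baseline visit and baseline measure do not.

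**2. A single eye.** Section 5.10 allows dispensing at 20/30 with the lens, and section 5.10.3 requires 20/25 or better by manifest refraction. Take the line sequence 20/15, 20/20, 20/25, 20/30 (an assumption). An eye stable at 20/30 with the lens that over-refracts to 20/20 scores 0 lines like for like, but a 2-line loss under 8.5. A stable 20/25 eye that over-refracts to 20/15 does the same.

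**3. The number of eyes.** The plan's own figures reproduce: with about 15% drop-out, 50/0.85 = 58.8 and 25/0.85 = 29.4, against 60 and 30 planned for dispensing. Planned completers are 50 + 25 = 75 subjects, or 150 eyes (100 Test, 50 Control). Completers are the base here because section 8.7.6 says "Discontinued subject data will be analyzed separately from the completed subject data".

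**4. Size under a simple model.** The documents give neither the variability of acuity change nor the benefit of over-refraction, so both are assumed. Take change in logMAR as normal with no true change, SD s, threshold T = 0.20 and baseline benefit g:

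- P(loss) = P(Z > (T − g)/s)
- P(gain) = P(Z < (−T − g)/s)

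| Benefit g | P(loss), s = 0.10 | Range, s = 0.08 to 0.12 | Eyes of 150 (range) |
|---|---|---|---|
| 0 (like for like) | P(Z > 2.00) = 2.3% | 0.6–4.8% | 3 (1–7) |
| 0.025 (quarter line) | P(Z > 1.75) = 4.0% | 1.4–7.2% | 6 (2–11) |
| 0.05 (half line) | P(Z > 1.50) = 6.7% | 3.0–10.6% | 10 (5–16) |

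By arm at s = 0.10, the half-line case gives about 7 Test and 3 Control eyes, instead of 2 and 1. Gains fall from 2.3% to P(Z < −2.50) = 0.6%, about 3 eyes to 1.

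If two lines means 20/20 to 20/30, T = log10(30/20) = 0.176. At s = 0.10, losses then rise from 3.9% to 10.4% with the half-line benefit, about 6 eyes to 16.

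**5. Between arms.** An equal benefit gives equal rates. A half line in one arm and a quarter line in the other gives 6.7% against 4.0%, a false difference of 2.7 points.

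**6. Check with whole lines.** A second model, also on assumed inputs, counts whole Snellen lines. The share of eyes helped by over-refraction runs from 10% gaining one line to 40% gaining one line plus 10% gaining two; the retest SD runs from 0.5 to 1.0 line. Apparent losses are 1.7% to 22.6% under 8.5, against 0.1% to 6.7% like for like. The direction is the same and the range wider.

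**The case against.** The strongest reply has four parts.

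**The visit conflict may be only a label.** Fitting and Training/Dispensing read as one continuous sequence in section 6.2 and may fall on one day. That is possible, though each has its own Visit Date entry. It would soften the difference in visit but leave the difference in measure.

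**The 8.5 phrase is undefined.** It could mean acuity with the lens finally chosen after over-refraction, since section 6.2.2 allows up to three lenses per eye to optimise acuity. The gap would then be small or absent. This reading is strained, given that 6.2.2 and Table 3 separate the two measures. Even if accepted, the two sections still differ in their words and need aligning.

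**The size is assumed.** This stands. The normal model shifts every eye by the same fraction of a line, whereas Snellen acuity is counted in lines. The gain figure is weakest: dispensing requires 20/30 or better, so few eyes have room to gain two lines. On the full analysis set of up to 180 eyes the half-line counts would be 180 × 2.28% = 4.1 against 180 × 6.68% = 12.0. The 2.7-point difference needs a benefit that differs by lens and is about 1.3 of 50 Control eyes.

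**Little hangs on it.** The analysis is supporting, the mismatch applies to both arms, and 5.4.2 requires each 2-line change to be explained. With best corrected lens acuity also collected at follow-up, some false losses would be recognised. This also stands, but the step examines only flagged eyes and so cannot recover hidden gains.

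The blank Training/Dispensing cell in Table 3 is a minor point. Footnote f requires some acuity at every visit, with lenses, glasses or unaided, which neither secures the 8.5 baseline nor shows that it is not collected.

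**Conclusion.** The concern holds. The visible text of 5.4.2 and 8.5 conflicts on both the baseline visit and the baseline measure, and 8.5 as worded compares unlike readings. Confidence in this is high and rests on the text alone.

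The direction of the error, more apparent losses and fewer apparent gains, rests on over-refracted acuity being normally no worse than lens acuity. Its size is not known. A rise from about 3 to about 10 eyes of 150 is what a uniform half-line benefit and an SD of 0.10 logMAR would give, and other plausible inputs give smaller or larger figures.

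No bias between Test and Control follows unless the benefit differs by lens. The main comparison of acuity distributions at scheduled visits is untouched. This should be fixed before analysis, but it does not threaten the main efficacy comparison.

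**What to change.** State one baseline visit and one measure, matched at both time points, in both 5.4.2 and 8.5. The simplest form is:

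*Lens acuity without over-refraction at the Fitting visit, with the lens selected for dispensing, compared with lens acuity without over-refraction at the final study visit.*

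Best corrected lens acuity at Fitting against best corrected lens acuity at the final visit is equally coherent and could be shown as a separate table. Section 8.5 should also repeat the commitment in 5.4.2 to explain every change of at least 2 lines.

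The cost is about one sentence in each section. Table 3 already schedules both measures at Fitting and at scheduled follow-up, so there are no new data and no change to sample size.

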5.10 Study Subjects

The dispensed study population will include up to 90 subjects who require a bilateral vision correction (180 eyes) randomized into the study contact lenses in a ratio of two to one (2:1) Test to Control subjects. This should result in a study population of approximately 60 Test subjects and 30 Control subjects.

The completed subject population is expected to include at least 50 Test subjects and 25 Control subjects. There are no provisions for replacing randomized subjects who are discontinued from the study.

To be eligible for study material randomization, a subject must have ALL of the Inclusion Criteria and have NONE of the Exclusion Criteria for initial screening/subject history, refractive assessment and ocular health findings. To be eligible for lens dispensing, the subject must have at least 20/30 VA in each eye with the study lens and the licensed investigator must judge the fit as acceptable or optimal.

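### The only visible within-subject acuity-change comparison counts changes of 2 or more lines, so it says little about a half-line loss that develops after fitting; add the full line change beside the raw acuity comparison

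*Combined protocol and SAP*

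**What the plan says.** The main efficacy analysis in section 8.5 uses Snellen acuity at scheduled visits, "analyzed using the relative comparative distribution of the visual acuity reports across the Test and Control lens groups". That comparison has no cut-off. A second analysis is then added: lens acuity at the final visit against a starting lens acuity, with "the changes (≥ 2 line change) assessed and compared across the Test and the Control Lens groups". Section 5.4.2 describes the same addition: "All changes ≥ 2 lines of visual acuity will be explained and compared across the Test and the Control lens groups". Section 8.5 expects both analyses to show substantial equivalence, so the change comparison is one of two supports for the efficacy conclusion.

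The sections name different starting points. Section 5.4.2 uses lens acuity at the Fitting visit. Section 8.5 uses over-refractive lens acuity at Training-Dispensing. Table 3 (section 6.3.3) marks lens acuity and over-refraction at Fitting and at scheduled follow-up, but not at Training/Dispensing.

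Section 8.3 promises descriptive summaries by cohort at baseline, fitting and follow-up. Section 8.2 states "The completed subjects sample size for this study is planned to be 50 Test Lens subjects and 25 Control Lens subjects" and "Due to the limited sample sizes required for this study the power calculations and level of significance are not appropriate for calculation"; differences are to be judged clinically. Text after the efficacy paragraphs in 5.4.2 and 8.5 is redacted, and section 8.6.2 on secondary efficacy is not shown.

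**The concern.** A cut at 2 lines treats a change of 0 and a change of 1 line as the same. Eyes are dispensed only at 20/30 or better, so most changes are likely to lie below the cut. With 25 Control subjects, the expected number of Control subjects losing 2 or more lines is about 0 to 2. Similar low counts in the two arms are then likely even if Test acuity has drifted down by half a line, and section 8.5 would read them as support for equivalence. The full line change can be derived from data already collected.

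**Working it through.** **Inputs.** Completers: 50 Test and 25 Control (8.2). Dispensed: about 60 and 30 (5.10). Drop-out: about 15% (8.2). Acuity limit at dispensing: 20/30 (5.10.5, 6.2.2). Everything else is assumed, because the plan gives no effect, SD, alpha or test: one value per subject, whole Snellen lines, and a two-sided 5% test as a yardstick. Only losses are counted; the plan does not give a direction for its 2-line changes.

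**Step 1, the plan's own figures.** 50/(1 - 0.15) = 58.8, or 59. 25/0.85 = 29.4, or 30. 75/0.85 = 88.2, or 89. The plan's 60, 30 and 90 agree closely. It states no power to reproduce.

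**Step 2, one case by hand.** Take an SD of line change of 1.0, a mean change of 0 on Control and a loss of 0.5 line on Test after fitting. With whole-line recording, a recorded loss of 2 or more means an underlying loss of at least 1.5.

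- Control: 1 - Φ(1.5) = 6.7%, or 1.7 of 25.
- Test: 1 - Φ(1.5 - 0.5) = 15.9%, or 7.9 of 50.
- Exact Fisher power: 13%. A normal-approximation test gives 17%, so Fisher's conservatism is not the main cause.
- Mean change: SE = 1.0 × √(1/50 + 1/25) = 0.245. Power = Φ(0.5/0.245 - 1.96) = Φ(0.08) = 53%. The 95% CI half-width is 1.96 × 0.245 = 0.48 line.

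**Step 3, a range of settings.** Starting and final acuity are simulated as bivariate normal and rounded to whole lines. Starting acuity is limited to 20/30 at the worse end and 20/15 at the better end, with 1,500 trials per setting. Before rounding, the SD of change is SD × √(2(1 - r)). It runs from 0.7 × √0.4 = 0.44 to 1.0 × √1.2 = 1.10 lines. Power for a half-line Test loss at the final visit only:

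| SD / correlation | 2-line loss (Fisher) | Full line change (t) | Raw final acuity (Wilcoxon) |
|---|---|---|---|
| 0.7 / 0.4 | 7.1% | 63.9% | 72.7% |
| 0.7 / 0.6 | 1.2% | 78.4% | 75.0% |
| 0.7 / 0.8 | 0% | 91.3% | 74.8% |
| 1.0 / 0.4 | 12.3% | 41.3% | 45.6% |
| 1.0 / 0.6 | 9.2% | 54.0% | 46.1% |
| 1.0 / 0.8 | 0.4% | 73.2% | 46.5% |

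Repeat runs differ by a few points; 0-12% and 41-92% cover them. The Control rate of 2-line loss is 0.1% to 7%, at most about 1.8 of 25. With no true difference, the full-scale tests reject 4.7% to 5.6% of the time and the 2-line count 0% to 2.7%.

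**Step 4, a one-line loss after fitting.** In the same model the 2-line count has about 57-79% power, the full line change 94-100%, and raw final acuity at least 96%. The simpler model of Step 2, with an SD of change from 0.5 to 1.5, gives 44-77% for the count. The count's figure depends on whole-line recording: if the underlying loss must reach 2.0 lines, it falls to 0-36%.

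**Step 5, a half-line loss present from first wear.** Section 6.2.2 randomizes first, then places the assigned lens and measures acuity after 10 minutes. Fitting acuity is therefore already an outcome of the assigned lens. With the same half-line loss at both fitting and final visits, power is:

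- full line change: 5-6%, about the false-positive rate;
- final acuity adjusted for fitting acuity: 12-42%, with an estimated loss of only 0.16 to 0.33 line;
- raw final acuity: 48-75%.

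**The case against.** The strongest reply is that the full acuity scale is already used where it counts. The raw distribution is the main comparison, and the 2-line count is an addition. The section 8.3 summaries go further: for completers with both values, the follow-up mean minus the fitting mean is the mean change, so the point estimate can be worked out from planned tables. In the two settings with correlation 0.4, raw final acuity beats the full line change. All of this stands. What the visible plan lacks is the distribution of within-subject change and the precision of the difference between arms.

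A second reply is that no test is planned, so power is beside the point. This stands in part. The power figures rest on assumed SDs and correlations and serve only as a yardstick. But clinical judgment on counts of 0 to 2 Control subjects faces the same shortage of information.

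A third is that 2 lines is a useful clinical flag. That is accepted, and the fix keeps it.

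A reader might infer more than the documents support:

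- *The trial cannot see a general loss of acuity.* It can, through the raw comparison.
- *A one-line loss is almost undetectable by the count.* With whole-line recording it is not (Step 4).
- *No full-scale change analysis exists.* Redaction and the missing section 8.6.2 limit the statement to the visible text.
- *Change from fitting should become the basis of the equivalence judgment.* Step 5 shows that it would miss a loss present from first wear.

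**Conclusion.** The point holds in a limited form. For a half-line Test loss that develops after fitting, the visible change comparison has about 0-12% power at 50 versus 25 subjects, against about 41-92% for the full line change. For a one-line loss it has about 57-79% against 94-100%: less sensitive, but not blind. These figures assume SD 0.7 to 1.0 line, correlation 0.4 to 0.8, one whole-line value per subject and a two-sided 5% yardstick, none of which the plan supplies.

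Low and similar counts of 2-line change should therefore carry little weight as evidence of equivalence in change. The full-scale table is a worthwhile, cheap supplement to the raw acuity comparison and does not replace it.

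**What to change.** 1. Reconcile sections 5.4.2, 8.5 and Table 3 so that one starting visit and one measure (lens acuity or over-refracted lens acuity) are named, and the data collection matches.
2. Keep the listing, explanation and count of changes of 2 or more lines. Keep the raw acuity distribution at scheduled visits as the main efficacy comparison.
3. Add a by-arm table of signed line change from the starting lens acuity to the final visit, in one-line steps. Report the Test minus Control difference in mean line change with a 95% CI, using one value per subject or a method that allows for paired eyes.
4. State that this table measures change after fitting only, because the starting acuity is taken on the assigned lens after randomization, and that it does not replace the raw comparison in the equivalence judgment.
5. If a baseline-adjusted comparison of final acuity is wanted, adjust for an acuity collected before randomization at the Initial visit: manifest-refraction or habitual-lens acuity.

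The cost is SAP wording and one extra table, with no new visits, subjects or measurements beyond whatever the reconciliation in item 1 settles. The downside is that a difference below 2 lines may appear and need clinical judgment.

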8.7 Additional Statistical Consideration

8.7.1 Interim Analysis

There will not be any interim analysis for this study.

